### **5.1.2.2 PrEP Comparison Component**

Maternal participants in Cohort 1 of the PrEP Comparison Component will take FTC/TDF through pregnancy and for 26 weeks postpartum, beginning on the day of enrollment and continuing through the day of the Week 26 postpartum visit.

Maternal participants in Cohort 2 of the PrEP Comparison Component who declined PrEP initiation during pregnancy will not take FTC/TDF for the duration of the study unless they undergo a step change and enter Cohort 2/Step 2.

Maternal participants in Cohort 2/Step 2 of the PrEP Comparison Component will take FTC/TDF for a variable duration, depending on timing of Step 2 entry. The duration will begin on the day of enrollment in Step 2 and continuing through the day of the Week 26 postpartum visit.

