## 6.2 PrEP Comparison Component

### 6.2.1 PrEP Comparison Component Maternal Screening, Enrollment and Follow-up Visits

Refer to [Section 4.5](#) for a description of the study recruitment, screening, and enrollment process. Women will be evaluated for potential participation with a gestational age that will permit study enrollment before 32 completed weeks. Infants will enroll into the PrEP Comparison Component, *in utero*, at the time their mothers enter the study. Infants will have study visits at birth, and 6, 14 and 26 weeks after birth.

Screening may be initiated after informed consent is obtained. All screening procedures except for sample collection for HIV RNA are expected to be performed within 30 days prior to study entry. Screening evaluations may be repeated during the 30-day period, with the latest outcomes used for eligibility determination. A HIV negative NAT test result, from a specimen collected within 14 days prior to enrollment, is required prior to entry. Multiple screening visits may be conducted within the 30-day time frame to complete all required procedures. If the 30-day screening period is exceeded, the screening process may be repeated. For potential participants who do not meet the eligibility criteria, screening may be discontinued once ineligibility is determined.

- Maternal creatinine testing is required in relation to the eligibility criteria in [Section 4.1.2.4](#) and to select follow up and step change visits; as soon as the creatinine test result is obtained for a given visit, the estimated CrCl rate should be calculated using the Cockcroft-Gault formula, and all results should be graded for severity as specified in [Section 7.2.1](#), and assessed for clinical significance concurrent with all other laboratory test results.

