- Fetal ultrasound should be performed during the study screening period to estimate gestational age and to assess for multiple gestation. Specific biometric measurements (e.g., crown-rump length, femur length, biparietal diameter, head circumference, abdominal circumference) to ensure that gestational age estimate is consistent across sites will be documented. Biometry from the ultrasound will subsequently be used to confirm (or change) the gestational age at study entry and gestational age at delivery. If ultrasound is performed during the screening period, results must be considered for purposes of eligibility determination. For example, if ultrasound indicates multiple gestation during the screening period, the mother (and her fetuses) should not be enrolled. Because ultrasound-based gestational dating is more accurate the earlier a woman is in her pregnancy, the prior ultrasound results will be used to meet this requirement, provided that a report of biometric measurements is available as documentation.

PrEP Comparison Component Maternal Screening Visit Procedures		
Administrative and Regulatory		
 
• Obtain written informed consent for PrEP Comparison Component Screening and Enrollment
 
• Assign participant identification number (PID)
 
• Obtain screening number from SES
 
• Assess eligibility for screening
 

Behavioral and Counseling		
 
• iNSC [see Section 5.3.2]
 

Clinical		
 
• Obtain available medical records and medical/medication history
 
• Perform complete maternal physical exam
 

Laboratory	Blood	
Collect blood for:
 
 
• HIV RNA test
 
• Rapid HIV test
 
• CBC with differential
 
• ALT, Creatinine, and CrCl
 
• Hepatitis B surface antigen
 
• Glucose (random)
 

	Urine	
Collect urine for:
 
 
• Urinalysis (protein and glucose)
 

Other	Ultrasound	Review medical records for results of any fetal ultrasound performed during this pregnancy to determine gestational age. If none are available, or if documented results are not adequate for study purposes, schedule ultrasound so that results are available prior to enrollment.
Study Drug		Not applicable

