Laboratory	
Collect blood for:
 

• HIV RNA test

• Store plasma for HIV drug resistance testing

• Rapid HIV test [see Section 6.3 in the event the test is (+)]

• Baseline TFV-DP level (DBS)

• Syphilis testing

• HSV2

 
Collect vaginal swab or urine for:
 

• Chlamydia and gonorrhea

 
Collect vaginal swab for:
 

• Microbiome

 
Collect rectal swab (if consented) for:
 

• Microbiome

Study Drug	
Cohort 1 only:
 

• Prescribe and dispense study drug

 A negative test result must be available prior to enrollment.

 Baseline sample must be collected prior to ingestion of study drug for Cohort 1 participants; the sample for Cohort 2 participants can be collected at any time and is required to confirm the participant is not receiving PrEP as standard of care.

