## 6.2.1.2 PrEP Comparison Component Maternal Antepartum Week 4, 8, 12 (during pregnancy)

The Antepartum (AP) Week 4, 8 and 12 visits are targeted to take place on Study Days 28, 56 and 84 respectively, counted from the date of study entry as Day 0, with an allowable window of  $\pm 7$  days. A negative rapid HIV test result at each visit must be available, for participants in Cohort 1 and Cohort 2/Step 2, prior to prescribing study drug.

In addition to the standard of care HIV prevention package provided and routine safety evaluations for all study participants at these visits, adherence and acceptability assessments are performed in Cohort 1.

Participants in Cohort 1 and Cohort 2 may deliver prior to completion of the AP Week 8 or Week 12 visit. If so, evaluations indicated for the AP Week 8 and Week 12 visit should be conducted in addition to the evaluations required for the Maternal Labor and Delivery Visit (Week 0) ([Section 6.2.1.4](#)). In those cases, the visit window of the L&D visit (+14 days) will apply.

Note that women who are selected for and consent to participation in the Qualitative In-Depth Interview during pregnancy may be scheduled for their interview at or after the Week 12 visit. See [Section 6.2.1.8](#) for details about this visit.

PrEP Comparison Component Maternal AP Weeks 4, 8 and 12 ( $\pm 7$ days)		
Behavioral and Counseling		
 
CASI and COVID-19 questionnaire [see Section 6.16]
 
 
Week 12:
 
 
Qualitative IDI Visit [see Section 6.2.1.8]
 
 
Cohort 1 and Cohort 2/Step 2 only:
 
 
iNSC with drug level feedback [see Section 5.3.2]
 
 
Cohort 2 only:
 
 
iNSC [see Section 5.3.2]
 
Assess for social harms [see Section 13.6]
 

Clinical		
 
Obtain interim medical/medications history
 
Perform targeted physical exam
 
Identify/review/update adverse events
 
Perform additional evaluations per Section 8 and/or if clinically indicated (consult CMC if indicated)
 

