ALT, creatinine, CrCl	4mL		4mL		4mL	4mL	4mL	4mL		4mL	4mL	
Hepatitis B surface antigen	3mL										3mL	
Syphilis		1mL									1mL	
HSV2		1mL									1mL	
Glucose (random)	1mL											
Chlamydia/gonorrhea (vaginal swab or urine)		X									X	
Microbiome (rectal swabs); if consent provided		X			X  (EGA 34-38/40 weeks)				X		X	
Microbiome (vaginal swab)		X			X  (EGA 34-38/40 weeks)				X		X	
Vaginal secretion sampling for drug level					X  (EGA 34 -38/40 weeks)				X		X	
Urinalysis (protein and glucose)	X											
Ultrasound	X											
DXA scan (Hip, Lumbar Spine) 								X			X	
Pregnancy Test 										X	X	
Total maximum blood volume	15mL	12mL	14 mL	10mL	14mL	14mL	14mL	14mL	10mL	18mL 	20mL 	

 CASI is done at Week 26 visit only; CASI is not required at early D/C.

 If positive refer to [Section 6.3.1](#) and [Appendix IID](#) for additional procedures.

 Store plasma for HIV drug resistance testing at all visits indicated EXCEPT Screening.

 Blood collected for other tests will be used for the rapid HIV test; collection of additional blood is not required.

 Collect sample at any visit which occurs at an estimated 34 – 38/40 weeks' gestation.

 DXA scan at Wk 26/Exit and early D/C (as applicable) must be preceded by a pregnancy test.

 Urine (5mL) or blood (1mL) tests are acceptable. The total blood volume shown above accommodates collection of 1mL of blood, if needed. Note: *Pregnancy testing may be done prior to the DXA scan at Wk 26/Exit and Early D/C and does not need to be repeated.*

As per [Section 6.5](#)

## Appendix IIB (Schedule of Evaluations): Maternal PrEP Comparison Component Cohort 2

MATERNAL PROCEDURES:	SCR	Entry	Wk 4	Wk 8	Wk 12	Wk 24	Wk 36	L&D	PP Wk 6	PP Wk 14	PP Wk 26 / Exit and Early D/C	Step Change	
												Visit 1	Visit 2
Informed Consent	X												
Medical and Drug History	X	X	X	X	X	X	X	X	X	X	X	X	X
Physical Examination	X	X	X	X	X	X	X	X	X	X	X	X	X
Study drug dispensing													X
Assess for social harms			X	X	X	X	X	X	X	X	X	X	X
iNSC	X	X	X	X	X	X	X	X	X	X	X	X	X
CASI evaluations and COVID-19 questionannire		X	X	X	X	X	X			X	X 	X	X
Qualitative IDI							X				X		
HIV RNA  ; store plasma for HIV drug resistance testing 	4mL	6mL	6mL	6mL	6mL	6mL	6mL	6mL	6mL	6mL	6mL	6mL	
Rapid HIV 	X	X	X	X	X	X	X	X	X	X	X		X

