### **Visit Scheduling and Procedural Considerations**

- The allowable visit windows for all maternal and infant follow-up visits are extended by  $\pm 7$  days, as follows:
  - Maternal antepartum visits at Weeks 4, 8, and 12: allowable visit window is expanded to  $\pm 14$  days.
  - Maternal antepartum visits at Weeks 24 and 36: allowable window is expanded to  $\pm 21$  days.
  - Maternal Labor and Delivery Visit and Infant Birth Visit: allowable window is expanded to up to 21 days after delivery/birth.
  - Maternal and Infant PP Weeks 6, 14, and 26: allowable visit window is expanded to  $\pm 21$  days.
- DXA scans are required at the Maternal Labor and Delivery Visit, Infant Birth Visit, and Maternal and Infant Week 26 visits. It is understood that sites may not be able to conduct the maternal and/or infant DXA scans on the same date as the other evaluations for these visits, and may not be able to arrange a scan within the corresponding visit windows. Sites should make every effort to schedule the DXA scan to take place within these windows, but up to 28 days is allowed.
- Sites may make use of these expanded allowable visit windows as needed, however, the visit windows specified in protocol [Section 6](#) remain the target and sites are encouraged to continue scheduling within these target windows whenever possible. Sites should consider current or anticipated operational disruptions or closures when scheduling visits and should schedule visits early or late in the allowable window, as appropriate. Visits conducted outside of allowable windows are also preferred to missed visits
- If it is not possible to conduct study visits in-person at the study site, visit procedures may be performed off-site or remotely (e.g., by telephone) as described below. Site investigators must ensure that standard operating procedures (SOPs) are in place for off-site and remote procedures.

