3.2 Primary Outcome Measure(s) for PrEP Comparison Component

PrEP adherence:

- TFV-DP drug concentration level in Dried Blood Spots (DBS)

Maternal Adverse Events:

- Maternal Grade 3 or higher adverse events (signs, symptoms, labs, and diagnoses)
- Maternal Grade 2 or higher chemistry abnormalities

Adverse Pregnancy Outcomes:

Composite outcome of

- Spontaneous abortion (occurring at <20 weeks gestation)
- Stillbirth (occurring at ≥ 20 weeks gestation)
- Preterm delivery (<37 completed weeks' gestation)
- Small for gestational age (<10th percentile using **INTERGROWTH-21st** norms and ultrasound derived gestational age at delivery)

Infant Safety:

Infant Adverse Events

- Infant death within the first 26 weeks of life
- Infant Grade 3 or higher adverse events (signs, symptoms, labs, diagnoses) reported between birth and 26 weeks postpartum

Infant Growth and Development

- Infant bone mineral content based on DXA scan of the whole body (WB-BMC) at birth and lumbar spine (LS-BMC) at birth and 26 weeks postpartum
- Infant creatinine and CrCl rate at birth and 26 weeks postpartum measured by Schwartz equation
- Infant length for age z-score at birth and 26 weeks postpartum

4 Definitions

Baseline

Maternal baseline is defined as the measurement on or closest to the study entry date, and infant baseline is defined as the measurement at birth. For the PrEP Comparison Component analyses characterizing the proportion with optimal adherence to PrEP among women in Cohort 2 who subsequently decide to initiate PrEP, baseline is defined as the date initiating PrEP.

Visit Windows for Analysis

All analyses summarizing or referring to data by visit week include a visit window around the applicable study visit week. For maternal antepartum study visit weeks 4, 8, and 12 the visit window is +/- 14 days. The visit window is +/- 21 days for antepartum visit weeks 24 and 36. The Labor and Delivery/Infant birth visit may occur as soon as possible after delivery through 21 days postpartum. The visit window is +/- 21 days for the maternal and infant 6- week postpartum, 14-week postpartum, and 26-week postpartum visits.

Analysis Sets

PK Component:

- **PK Adherence Set:** All maternal participants on PrEP, including those in Group 1 and those in Group 2

PrEP Comparison Component:

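### The SAP's two-sided maternal baseline rule can make a Week 4 on-PrEP value the Cohort 1 baseline; the effect is confined to baseline summaries and any model that uses an affected variable

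*SAP*

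**What the plan says.** The rule, in SAP section 4 (Definitions, Baseline), is: "Maternal baseline is defined as the measurement on or closest to the study entry date". It does not require the measurement to precede entry or the first dose, and it does not say what to do when two measurements are equally distant. A separate baseline, the date of starting PrEP, is given only for adherence analyses of Cohort 2 women who start PrEP later.

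The protocol sets the timing of the measurements:

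- **Screening (6.2.1).** "All screening procedures except for sample collection for HIV RNA are expected to be performed within 30 days prior to study entry". The screening blood list includes "ALT, Creatinine, and CrCl".
- **Entry (6.2.1.1).** The blood list has HIV RNA, stored plasma, rapid HIV test, TFV-DP, syphilis and HSV2, and no safety chemistries. Appendix IIA agrees: the row "ALT, creatinine, CrCl" has a volume at screening and at Week 4 and is blank at Entry. The one pre-dose requirement concerns the TFV-DP dried blood spot (DBS): "Baseline sample must be collected prior to ingestion of study drug for Cohort 1 participants".
- **Week 4 (6.2.1.2).** The dates of the first three antepartum follow-up visits are given as "targeted to take place on Study Days 28, 56 and 84 respectively, counted from the date of study entry as Day 0"; each may fall up to 7 days either side. Chemistries are drawn at Weeks 4 and 12. Appendix X widens the window to 14 days either side at disrupted sites, and SAP section 4 uses 14 days for analysis.
- **Start of drug (5.1.2.2).** Cohort 1 takes FTC/TDF "beginning on the day of enrollment and continuing through the day of the Week 26 postpartum visit".

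**The concern.** A baseline should describe a participant before the exposure under study. For the three chemistries no Entry measurement exists, so among scheduled draws the rule always chooses between one pre-drug value (screening) and one value taken four weeks or so into follow-up. In Cohort 1 the later value is on drug. In Cohort 2 it is off drug, unless the woman has already moved to Step 2. The same words therefore define different quantities in the two cohorts. An unscheduled, clinically indicated draw between entry and Week 4 could also be selected.

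The CASI needs no coincidence of dates. It is not collected at screening, so if the Entry questionnaire is missing, the nearest scheduled one comes after entry, ordinarily at Week 4. By then Cohort 1 has been given PrEP and has had weekly two-way SMS support (protocol 5.3.2). In the same way, a missing Cohort 1 Entry DBS would be replaced by an on-drug concentration.

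This matters because the cohorts are self-selected, and protocol 9.2.1 relies on measuring and adjusting for confounders. Maternal baseline characteristics are to be reported to ClinicalTrials.gov (SAP section 7), baseline predictors enter the exploratory adherence models (SAP 6.3.1), and supplemental safety analyses adjust for confounders that are not named (SAP 6.3.2 to 6.3.4).

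**Working it through.** The plan states no figure to reproduce. The check counts which pairs of permitted days lead the rule to select Week 4.

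**Inputs**

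- Screening chemistry *s* days before entry, *s* = 1 to 30 (protocol 6.2.1).
- Week 4 chemistry *w* days after entry: Day 28 exactly; Days 21 to 35 (protocol 6.2.1.2); Days 14 to 42 (SAP section 4 and Appendix X).
- PrEP begins on Day 0 in Cohort 1, so every *w* in these ranges is on or after the start of drug.

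**Rule.** Week 4 is strictly closer when *w* < *s*. A tie occurs when *w* = *s*.

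**Example.** With chemistries 25 days before entry and Week 4 on Day 21, the distances are 25 and 21, so the Day 21 value becomes baseline.

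**Formula.** If the earliest Week 4 day is *a* and the window extends past Day 30, each *s* from *a* + 1 to 30 contributes *s* − *a* pairs. The total is *n*(*n* + 1)/2 with *n* = 30 − *a*.

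- Protocol window: *n* = 30 − 21 = 9, so 9 × 10/2 = 45 pairs out of 30 × 15 = 450.
- SAP window: *n* = 30 − 14 = 16, so 16 × 17/2 = 136 pairs out of 30 × 29 = 870.
- Day 28 exactly: only *s* = 29 and *s* = 30, so 2 out of 30.

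| Week 4 timing | Strictly closer | Share | Ties | Screening lags that can be displaced |
|---|---|---|---|---|
| Day 28 exactly | 2 of 30 | 6.7% | 1 | 29 to 30 days |
| Days 21 to 35 | 45 of 450 | 10.0% | 10 | 22 to 30 days |
| Days 14 to 42 | 136 of 870 | 15.6% | 17 | 15 to 30 days |

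**Short screening lag.** If *s* is at most 14, no pair has *w* < *s*, because *w* is never below 14. One tie remains: 14 days before against Day 14.

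**After the fix.** With baseline limited to measurements on or before entry and before the first dose, the counts are 0 of 450 and 0 of 870.

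The shares treat all permitted days as equally likely. The documents give no distribution of screening lags or Week 4 dates, so the counts show that substitution is possible, not how often it will happen.

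**Where baseline is used.** Maternal creatinine and CrCl are graded on absolute value, not on change from baseline (protocol 7.3.3). The primary maternal safety estimate is a Poisson incidence rate ratio with no baseline covariate named (SAP 6.3.2). The entry characteristics to be compared between cohorts (SAP section 5) are demographic, obstetric, psychosocial, sexual behavior and partner variables; no chemistry is listed. The one explicit covariate list (protocol 9.2.6, Other Objective 2.4.1) is behavioral and contextual.

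**The case against.** The strongest reply is that no analysis named in the documents uses a maternal baseline creatinine, CrCl or ALT. The safety endpoints do not need one, no maternal change-from-baseline laboratory analysis is planned, and neither the entry comparison nor the listed covariates contain chemistries. This stands, and it sets the limit of the point.

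The reply has four further parts:

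- **Timing.** HIV RNA must be collected within 14 days of entry and is on the same screening blood list. If the chemistries are drawn with it, Week 4 is never strictly closer. Repeat screening draws would also shorten the lag. This stands as a mitigation, but screening may be split over several visits, and nothing requires the chemistries to accompany the HIV RNA sample.
- **Windows.** Appendix X keeps the standard windows as the target. True, but SAP section 4 applies the wider window to all analyses by visit, and the standard window already allows substitution.
- **CASI and DBS.** Both are required on the day of enrollment, so substitution needs a missed procedure, and no planned analysis uses the Entry DBS as a covariate. That is fair. For these two items the realistic route into an analysis is a missing Entry CASI, and the predictor models it would enter are labelled exploratory.
- **Analysis Implementation Plan.** It may narrow the derivation. It is not among the documents, and the SAP is where the term is defined.

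A reader might infer that the cohorts' renal baselines will be non-comparable and that adjusting for them will remove part of the PrEP effect. The documents do not support that: no renal baseline comparison or adjustment is specified. Protocol 1.2 describes the filtration decrease on TDF as small and reports no clinically significant creatinine elevations in PrEP trials. Eligibility also requires CrCl of at least 90 mL/min at screening in both cohorts.

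**Conclusion.** The rule as written is wrong for this schedule, and the correction is minor but worthwhile. Followed literally, it can label an on-drug measurement as baseline in Cohort 1, and it leaves ties unresolved. Under equally likely days the share is about 7% at Day 28, 10% over the protocol window and 16% over the SAP window, and zero if the chemistries are drawn within 14 days of entry.

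Higher shares can be obtained by fixing Week 4 on its first permitted day: 9 of 30 lags (30%) at Day 21 and 16 of 30 (53%) at Day 14. These hold only for women seen on that day, again with uniform lags, and should not be read as the proportion of the cohort affected.

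Nor should the point be read as bias in the primary maternal safety comparison, which does not use baseline. What is exposed is the baseline-characteristics table, if it includes an affected variable, and any exploratory predictor or confounder-adjusted model that does so. Confidence is high about the wording and the schedule. The practical size is unknown, because it depends on actual visit dates, on missing Entry questionnaires and on covariate choices that the SAP leaves open.

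**What to change.** Replace the maternal baseline sentence in SAP section 4 with: maternal baseline is the last non-missing measurement on or before the date of study entry and before the first PrEP dose; for Step 2 analyses, it is the last non-missing measurement on or before Step 2 entry and before the first dose; if there is none, baseline is missing and no later value is used. Carry the same rule into the Analysis Implementation Plan.

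The cost is one sentence and a small change in the derivation code. No chemistry baseline is lost, because eligibility requires a screening value. A few missing Entry CASI or DBS values would stay missing and should be reported as such.

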6.2 Secondary Estimand – PK Component

Secondary Objective 1: To compare TFV-DP concentrations observed in pregnant and postpartum women	
Estimand description	Maternal Steady state TFV-DP concentrations at Week 12
Treatment	
 Daily oral PrEP (200 mg FTC/ 300 mg TDF) during pregnancy and/or postpartum administered through direct observation.
Target population	Analysis set
Women who are pregnant and test HIV-negative, are 16-24 years of age, enrolled during a singleton pregnancy at 14-24 weeks' gestation or postpartum within 6-12 weeks after delivery, and express willingness to take daily oral PrEP under direct observation for 12 weeks	PK Adherence set: Women initiating PrEP
Variable(s)	Outcome measure(s)

TFV-DP drug concentration level	1. TFV-DP drug concentration level from Dried Blood Spots (DBS) measured at week 12 among pregnant women 2. TFV-DP drug concentration level from Dried Blood Spots (DBS) measured at week 12 among postpartum women.
Handling of intercurrent events	Handling of missing data
Discontinuation of PrEP: Only visits occurring prior to discontinuation of PrEP will be included. (While on treatment strategy)	Missing data could occur in the following situations: 
• Missing visit(s) when DBS would have been collected• Missing drug concentration results due to sample collection or processing issues. If a single specimen is missing at week 12, and a specimen is available at week 11, sensitivity analyses will be conducted including the results from the analysis of the 11-week specimen.
Population-level summary measure	Analysis approach
Difference in median TFV-DP concentration levels at Week 12 between pregnant (Group 1) and postpartum (Group 2) groups.	In each of the two groups (antenpartum and postpartum groups), the median and IQR of steady state concentration (Css), defined as the TFV-DP concentration observed at week 12 corresponding to 6-7 day/week adherence ("optimal adherence"), will be calculated for each group. Differences in median Css between the antenpartum and postpartum groups will be evaluated using Wilcoxon Rank Sum tests.

